**Statistical Considerations**

**1. Is stratification/randomization involved? Yes**

**► IF YES, describe the stratification/ randomization scheme.**

1. Randomization will be done at the Screening Visit and will be performed by simple randomization schedule (like flipping a coin)
2. Randomization will not be blinded; it will determine the order of the Experimental and Control Admissions after the initial 14-28 days of Data Collection

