**Figure 2: Example of web-based diabetes management systems used for data upload (Diasend top, CareLink bottom)**

### **Visit 3 and 4: Research Admission (i.e., Hotel).**

The Experimental and Control Admission will be separated by at least 48 hours with a maximum of 100 days. The order of these two visits will be randomly selected. Subjects will be admitted to the research location at approximately 9:00AM and will be discharged after approximately 24 hours.

All procedures will be the same for Visit 3 and Visit 4 with the following exception:

- Insulin Boluses during the Control Admission: All meal and correction boluses during the control admission will be per the subject's usual insulin parameters. The two admissions will use consistent insulin-to-carbohydrate ratio, correction factor, and basal profiles.
- Insulin Boluses during Experimental Admission: The dinner meal bolus will be determined with the use of the SI-informed bolus calculator during the Experimental Admission. The calculations will be performed on a study smartphone (Diabetes Assistant, DiAs), approved by the study MD, and subsequently communicated to the subject. The suggested insulin bolus will be administered through the subject's personal insulin pump. The study physician will override the insulin dose computed with the use of the SI-informed bolus calculator at any time if he/she considers it is not safe for the participant subject in the following way:

- 1 The dinner insulin dose suggested by the SI bolus calculator will be  $\pm 30\%$  of the dose that the subject should receive while using his/her own insulin pump bolus calculator (usual care). This is by design of the SI bolus calculator.
- 2 If the licensed endocrinologist conducting the study considers the dinner dose suggested by the SI bolus calculator to be unsafe he/she will override this dose.
- 3 In order to avoid bias between the physicians involved, every effort will be made to have the primary MD supervising all the experimental admission.

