- 4 Since the visits will be randomized, regardless of when the experimental visit occurs, the MD supervising the trial will look at the standard dose suggested by the DiAs system using the participant's insulin therapy parameters and will indicate that dose (control) if the assigned insulin dose suggested by the SI bolus calculator is deemed to be unsafe. This will be equal regardless of who is the physician supervising the visit. In this way any bias will be avoided since the criteria used by all MDs listed on this protocol will be the same.
- 5 During both visits, control and experimental, the same procedures will be followed. Therefore, the dose suggested by the DiAs system using the participant's insulin therapy parameters during the experimental admission to override the dose suggested by the SI bolus calculator, should be consider safe and usual care for that particular participant.

Visits 3 and 4 will be fully supervised by a research team located at the hotel and gym at all times and will be monitored and supervised by the primary physician. In the event that the primary physician could not be available for a particular visit, the backup MDs will cover. The team will consist of a minimum of one registered nurse (trained in the execution of the protocol as well as in the management of hypo- and hyperglycemia) and a technician (trained in the use and maintenance of the DiAs system). In addition, one of the study medical physicians, primary MD, and one senior engineer will be on call during the entire admission, with backup physicians and engineer available if the primary contact is unable to be reached.

The CGM used in the study is FDA-approved for the non-adjunctive measurement of blood glucose and will be remotely monitored in real-time during the entire admission (including exercise) by the study team via the DiAs Web Monitoring platform. The CGM readings will be the primary source of blood glucose levels. There are no protocol fingerstick blood glucose measurements other than at times of CGM calibration and if directed by the study team.

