#### **Procedures at beginning of Research Visit**

1. Subjects will meet the study team and check in to the research location at approximately 09:00AM, after a morning breakfast consumed at home per regular subject's habit.
2. The study team will confirm that the subject brought his/her insulin, insulin pump supplies, and regular medications. The study team will also confirm the absence of a febrile illness and may reschedule the admission if this criterion is not met.
3. Female subjects of childbearing potential will perform a urine pregnancy test. If positive, the subject will discontinue study participation. The subject will be asked to seek confirmation of the test and the appropriate medical care.
4. The study team will take the subject's vital signs, measure ketone concentration using the study ketone meter, and connect the DiAs system to the subject's CGM transmitter via Bluetooth connection (the DiAs is not connected to the subject's insulin pump, only to the CGM).

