#### **Glycemic Guidelines during Research Visit**

1. Upon arrival, the subject will be asked to check the CGM reading and ketone concentration using the study ketone meter. If CGM <70 mg/dL or >300 mg/dL or ketone test is >0.6 mmol/L, study physician will suggest appropriate treatment. The study subject may continue participation in the trial once CGM is between 70-300 mg/dL and ketone concentration ≤0.6 mmol/L.
2. If CGM >300 mg/dL for more than 1 hour or >400 mg/dL at any time, study physician will be notified to suggest appropriate treatment and ketones will be checked. If ketone

concentration is  $>0.6$  mmol/L, the study team will check the insulin pump infusion site and correction insulin will be administered per study physician judgement via the subject's insulin pump or study-supplied insulin pens. The study team will monitor CGM decay and ketones will be checked every 60 minutes until  $\leq 0.6$  mmol/L.

3. If ketone concentration is  $\geq 3.0$  mmol/L, the study subject will be discontinued, DiAs will be changed to Stopped mode, and appropriate medical treatment will be sought. If the subject is discontinued, he/she may repeat the admission at discretion of the PI.
4. If CGM  $<60$  mg/dL at any time, subjects will be given approximately 16 grams of fast-acting rescue carbohydrates. Study team will monitor CGM rise and will consider treating again if CGM  $<80$  mg/dL after 20 minutes. Hypoglycemic treatments can occur at any time per study physician request.
5. If CGM  $<80$  mg/dL at any time during the exercise session, subjects will suspend the exercise activity and take approximately 8-16 grams of fast-acting rescue carbohydrates. Study team will monitor CGM rise and will consider treating again if CGM  $<80$  mg/dL after 20 minutes. Exercise activity will resume once CGM  $\geq 80$  mg/dL.
6. Prior to the subject being discharged from the admission after either completing the study procedures or discontinuation, the CGM and ketones will be checked. The subject will be discharged once the CGM reading is between 80-250 mg/dL and ketone concentration  $\leq 0.6$  mmol/L.

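### The bedside nurse is left aware of the arm after dinner without a stated need, while repeat rescue, physician-requested treatment and the timing of corrections are discretionary and can alter the primary LBGI

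*Combined protocol and SAP*

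**What the plan says.** Statistical Considerations, item 1, states: "Randomization will not be blinded; it will determine the order of the Experimental and Control Admissions". No other section masks the participant, nurse, technician or physician. Who knows the arm after dinner is not set out person by person; it follows from this statement and from the visit procedures.

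The section on Visits 3 and 4 says: "All procedures will be the same for Visit 3 and Visit 4 with the following exception", and the exception is how the boluses are set. In the Experimental Admission the dinner dose is calculated on DiAs, "approved by the study MD, and subsequently communicated to the subject", and then delivered through the participant's own pump. Its departure from the standard dose is capped at 30%. For the safety override, "the MD supervising the trial will look at the standard dose suggested by the DiAs system using the participant's insulin therapy parameters". DiAs is set up at both admissions, and "the DiAs is not connected to the subject's insulin pump, only to the CGM".

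The primary analysis (Statistical Considerations, item 4) compares CGM LBGI after dinner between the admissions. Under Power/Precision, Cohen's d from this pilot is to be the effect size for the main trial.

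Glycemic Guidelines, item 4, fixes a first rescue at CGM below 60 mg/dL. A second treatment is something the team is to consider if CGM is still below 80 mg/dL after 20 minutes. It adds: "Hypoglycemic treatments can occur at any time per study physician request". Procedures during Research Visit, item 9, bases corrections on CGM but gives no rule for when one is given after dinner.

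**The concern.** Once the dinner bolus is in, care is meant to be the same in both admissions. If those giving it know the arm, their discretionary decisions can differ by arm without anyone intending it. They may be quicker or slower to repeat carbohydrate, to ask the physician for treatment, or to suggest a correction.

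LBGI is computed from sensor data, so its measurement is not open to judgement. The glucose that the sensor records is. A low that is shortened or prevented by treatment never enters LBGI, and no later analysis can restore it. The planned tables would not show the difference either, because the number of hypoglycemia treatments, reported for the simulation in the Background, is not among the planned outcomes.

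What is at stake is the estimate handed to the main trial. The protocol guards against bias in the physician's override decision, but not in care during the hours that form the outcome.

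**Working it through.** **1. Is one handover feasible?** The Background and override item 4 show that DiAs yields the standard dose as well as the SI-informed dose. DiAs is connected to the CGM at both admissions and not to the pump, so any DiAs dose has to be passed on by a person. The Experimental route (DiAs calculates, physician approves, participant is told a dose) can therefore serve Control too. The glycemic guidelines are keyed to CGM and ketones, not to arm, so the nurse can follow them without knowing it.

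**2. Which post-dinner decisions are open?**

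| Decision | Where | Rule | Can it alter CGM LBGI? |
|---|---|---|---|
| First rescue | Glycemic Guidelines, item 4 | Fixed, CGM <60 mg/dL, same in both admissions | Yes, but not discretionary |
| Repeat rescue | same item | Team considers it if CGM <80 mg/dL at 20 minutes | Yes, discretionary |
| Extra treatment | same item | Physician request, no threshold | Yes, discretionary |
| Routine correction | Procedures during Research Visit, item 9 | CGM-based, timing not stated | Yes, discretionary |
| Extra fingersticks | same section, item 10 | Staff or participant choice | Not directly; LBGI is from CGM |

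**3. Who can be masked?**
- Nurse: yes.
- Participant: only in part. The participant's pump calculator gives the usual dose, which can be compared with a dose changed by up to 30%.
- Approving physician: no. The override requires sight of both doses.

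**4. The plan's own figure.** Enrolment: 15 / (1 − 0.40) = 25, as stated. The point does not depend on it. No alpha, power, standard deviation or effect size is given, so there is no power figure to reproduce.

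**5. How few treatments may be involved.** Assume that the simulated counts (34 control, 6 experimental, 6 hours after dinner) cover all 100 virtual subjects and carry over to 15 people. Then 34 × 15/100 = 5.1 and 6 × 15/100 = 0.9 treatments. A few treatments influenced by knowledge of the arm would be a large share of the total.

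**6. What a shift in d would do to the main trial (illustration only).** Assume a paired comparison, two-sided 5%, 80% power, with N = ((1.960 + 0.842)/d)² rounded up. Power at the true d is Φ(d√N − 1.960). With an assumed true d of 0.5:

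| Shift in d | d used | N | Power at true d = 0.5 |
|---|---|---|---|
| −0.2 | 0.3 | 88 | 99.7% |
| −0.1 | 0.4 | 50 | 94% |
| 0 | 0.5 | 32 | 81% |
| +0.1 | 0.6 | 22 | 65% |
| +0.2 | 0.7 | 17 | 54% |

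With a true d of 0.3, N falls from 88 to 50 or 32 for shifts of +0.1 or +0.2 (power 56% or 40%). With a true d of 0.8, it falls from 13 to 10 or 8 (72% or 62%).

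**7. Would the pilot reveal such a shift?** SE(d) = √(1/n + d²/(2n)). At n = 15 and d = 0.5 this is √(0.0667 + 0.0083) = 0.274, a 95% half-width of 0.54. For d from 0 to 0.8 the half-width is 0.51 to 0.58. A shift of 0.1 to 0.2 would not be visible.

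**The case against.** The other side has four good arguments.

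- **Bedside discretion is narrow.** First rescue is a fixed rule. Repeat rescue arises only after a first treatment, so it cannot prevent the initial low. Correction factor and basal profiles are the same in both admissions. This stands: what the nurse can influence is repeat rescue, the timing of corrections, and when to call the physician.
- **The freest route belongs to the physician.** After dinner, treatment above the fixed trigger comes at the physician's request, and the approving physician has seen both doses. This also stands. Masking the nurse alone does not close that route, which is why the fix separates dose approval from later requests where it can.
- **Participant masking is weak.** Participants estimate the dinner carbohydrates, know their own parameters and hold the pump that gives the usual dose. This stands; their masking is partial at best. The technician, on site with the nurse, would also know the arm.
- **This is an open pilot with a sensor endpoint, not powered for any outcome, and sampling error exceeds the shifts illustrated.** That lowers the priority. It does not remove the point, because a systematic shift passes into the main trial's effect size and costs little to reduce.

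A reader might infer a sizeable, computable bias in favour of the device. For example, assume the usual log-transformed risk function for LBGI (not printed in the documents) and early treatment that avoids 30 to 60 minutes near 58 mg/dL. That night's LBGI over 6 hours then falls by 0.61 to 1.84. If this happens on 1 to 3 more Experimental than Control nights out of 15, the mean moves by 0.61 × 1/15 = 0.04 to 1.84 × 3/15 = 0.37. Against the simulated difference of 2.4 − 1.3 = 1.1, that is 4% to 34%. The documents do not support this reading. The number of nights is invented. The primary analysis does not define its window; over the roughly 14 hours from dinner to discharge the same events give 0.04 × 6/14 = 0.02 to 0.37 × 6/14 = 0.16. The early treatment assumed is the physician's route, not the nurse's. The sign is also unknown: staff who expect lows after the unadjusted bolus could treat Control earlier.

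**Conclusion.** The concern holds in a limited form. The trial is fully open, the planned difference is a single dinner dose, and the protocol gives no reason for the bedside nurse to know which dose was released. Repeat rescue, physician-requested treatment and correction timing are discretionary and can alter the primary outcome. Openness is avoidable for the nurse, only partly avoidable for the participant, and unavoidable for the approving physician.

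The size and direction of any bias cannot be computed from the documents. The illustrations above rest on assumed values of d, assumed shifts, and simulated rescue counts carried over to people. They show only that a small shift would go unnoticed at n = 15 and could matter for the next trial. This is a cheap improvement that reduces bias in part. It is not a flaw that invalidates the pilot.

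**What to change.** - In Statistical Considerations, item 1, and in the section on Visits 3 and 4, state that both dinners use the same handover: the technician runs DiAs, the physician releases the assigned dose, and one dose figure is passed on without the arm or the alternative dose.
- State that the bedside nurse is not told the arm from dinner to discharge, and may be unmasked for safety at any time.
- Describe participant masking as partial. Ask participant and nurse to guess the arm at discharge, and report the guesses.
- Where existing cover allows, let a listed physician who did not approve the dinner dose handle post-dinner treatment requests. The sentences that aim for the primary physician to supervise the admissions need a matching line.
- Log the time, reason and requester of every post-dinner rescue and correction, and add their tabulation by arm to the planned analyses.

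The text describes the usual dose both as the DiAs standard dose and as the pump calculator's dose. The sponsor should reconcile the two, so that it is clear which figure is released at the Control dinner.

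Cost: protocol wording, a dose-release slip and a short log, using the existing team of nurse, technician and on-call physicians. Downside: masking is incomplete and may be broken by the participant or technician. The masking and logging change no dose, threshold or treatment rule.

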**► IF YES, who will generate the randomization scheme?**

Sponsor  
 UVa Statistician.  Answer/Response:  
 UVa Investigational Drug Service (IDS)  
 Other: : Center for Diabetes Technology (CDT) personnel

**2. What are the statistical considerations for the protocol?**

**Study Design:**

The study is designed as a 14-to-28-day at home Data Collection Period followed by two 24-hour admissions (Experimental and Control Admission) in a semi-controlled environment (i.e., hotel), performed in random order. During the entire duration of the study, subjects will be using their personal insulin pump, personal glucometer, a study CGM, study ketone meter, and a study activity tracker. The Data Collection Period is used to collect up to 28 days of CGM data, insulin and meal records, with the aim of building a 24-hour SI profile for the subject that will be used to modulate the insulin bolus during the Experimental Admission. On admission days, subjects will arrive at the hotel at approximately 9AM after a home breakfast per their normal routine; at approximately 12PM, they will be provided lunch, which will be followed by an exercise session at approximately 2:30PM. The exercise session will consist of three 15-minute bouts of moderate-intensity exercise (i.e., stationary bicycle). At approximately 7PM, subjects will be provided a controlled dinner; the SI-informed bolus calculator will be used in the Experimental Admission while standard therapy will be used in the Control Admission. Subjects will then be observed overnight and discharged the following morning.

**Study Objectives and Endpoint Definitions:**

The objective of the study is to test the safety and feasibility of the SI-informed bolus calculator. Overall and postprandial occurrence of hypoglycemia as measured by the Low Blood Glucose Index (LBGI) computed on CGM data, will be compared between the optimized bolus calculator (Experimental Admission) and standard therapy (Control Admission), with the purpose of assessing whether the optimized paradigm for insulin dosing allows to improve postprandial control after an afternoon exercise session.

**Power/Precision of the study to address major study endpoints:**

As a safety and feasibility study, this trial is not powered to a specific outcome. A sample size of 15 subjects has been chosen with the purpose of being able to compute the Cohen's  $d$  once the trial is completed. Cohen's  $d$  is defined as the difference between two means divided by a standard deviation for the data (standardized difference between two means), and will serve as effect size to appropriately power the subsequent main trial.

**3. Provide a justification for the sample size used in this protocol.**

The sample size is determined based on the fact that this study is a pilot trial. In prior studies, 15 subjects have also been considered by regulatory bodies as an appropriate sample size to demonstrate safety in transitional settings for CGM based insulin dosing, and existent literature suggests that a sample size of 10-30 participants is appropriate for pilot studies.

**4. What is your plan for primary variable analysis?**

We will compute CGM metrics with the primary outcome analysis of LBGI by CGM following dinner, comparing the Experimental Admission to Control Admission.

**5. What is your plan for secondary variable analysis?**

In addition, descriptive glycemic analyses for secondary efficacy measures will be tabulated for each subject based on CGM data, including:

- mean glucose
- percentage of readings in the target range of 70-180 mg/dL
- percentage of readings <70, 60, and 54 mg/dL
- percentage of readings >180, 250, and 300 mg/dL

**6. Have you been working with a statistician in designing this protocol? No**

**IF YES, what is their name?**

**7. Will data from multiple sites be combined during analysis? No. This is a UVa only study.**

**INSTRUCTIONS: IF YES, answer the following questions**

**7(a). Does the study involve randomization?**

**IF YES, will randomization be done at each site or among sites?**

**7(b). Has the sample size calculation considered the variation among sites?**

**7(c). When combining the data from multiple sites to assess the study results, is the effect of the treatment to be tested (or the association to be tested) assumed to be the same across sites or vary among sites? What is the modelling strategy?**

**7(d). Is there a common protocol used in all sites?**

**IF NO, how will differences among sites, such as those related to the implementation, inclusion criteria, patient characteristics, or other sites characteristics, be considered to assess the study results?**

#### **Study Procedures-Biomedical Research**

**1. What will be done in this protocol?**

##### ***Visit 1: Screening Visit.***

All subjects will be consented and receive a history and physical. Study eligibility will be reviewed. If a subject satisfies all the study inclusion criteria and does not meet any exclusion criteria, he/she will be enrolled in the study and randomized to the Experimental or Control Admission occurring first.

At the Screening Visit, the following procedures will be performed, and criteria will be checked and documented:

1. Signed and dated informed consent
2. Inclusion and exclusion criteria
3. Demographics (date of birth, gender, race and ethnicity)
4. Medical history
5. Details of the diabetic history: duration of disease (number of years), diagnosis details, current treatment (including basal rates or basal insulin dose(s), carbohydrate ratios, insulin sensitivity factors, target glucose, average total daily insulin, history of DKA, history of severe hypoglycemia, and self-monitoring blood glucose values)
6. Surgical history
7. Menstrual history (females) and sexual activity/contraception (females)
8. Allergies
9. Medications and supplements
10. Social history including drinking and smoking
11. Physical examination
12. Electrocardiogram (ECG)
13. Weight and height
14. Vital signs
15. Blood and urine testing for screening labs:
  - Hemoglobin A1c
  - Comprehensive chemistry panel
  - TSH
  - Pregnancy test: either urine or qualitative serum HCG in women with childbearing potential. If not performed, document reason (surgically sterile, postmenopausal)

If a study subject has had a recent physical exam (less than 6 months) and blood work done (less than one month), the study physician will have the discretion to repeat any test as needed. Once all results of the screening evaluations are available, a decision will be made to determine the subject's eligibility for the study or if one or more parts of the screening will have to be repeated. If at the first screening or repeated screening an exclusionary condition is identified, the study subject will be excluded from participation and referred to their primary care physician as needed. If the study subject is pregnant, the study physician will discuss the results of the urine/blood test with the subject, and the subject will be asked to seek confirmation of the test and the appropriate medical care. The screening visit will last approximately 2 hours. If the subject cannot schedule Visit 2 within 16 weeks of screening, screening labs, vital signs, and recent medical illness/medications will be re-evaluated. The study physician will have the discretion to repeat any test as needed. If a subject meets all the study criteria, he/she will be enrolled in the trial and randomized to begin the experimental or control admit first. Visit 2 may be completed at the conclusion of Visit 1 if all eligibility requirements are met.

All subjects will be advised to contact the study team in the event of a febrile illness within 48 hours of the study visits, so that the study visits can be rescheduled. All subjects will be given

instructions to bring all of their current medications and insulin pump supplies with them for use during or after the study visits.

